# Study Protocol and Statistical Analysis Plan

### **Patient selection**

Adult patients (age>18 years) receiving elective cardiac surgery requiring cardiopulmonary bypass were screened for eligibility from August-October 2021. Written informed consent was obtained from eligible patients prior to surgery. Patients were excluded if they had a nitroglycerin allergy, were taking oral phosphodiesterase inhibitors, were unable to tolerate microcirculatory flow image acquisition or did not have a pulmonary artery catheter for continuous cardiac output monitoring after surgery. Patients only received the study drug if they met the clinical criteria for circulatory shock, defined as having postoperative vasopressor-dependent hypotension or low cardiac output requiring inotropic support, with signs of end-organ injury (capillary refill time > 3 seconds, lactate > 2, SvO2 < 60%). A second cohort of patients were enrolled to serve as a preoperative control, which were matched to the experimental group for age, co-morbidities, and planned operation. Study data were collected and recorded using a well-established clinical database tool (REDCap, Vanderbilt University, Nashville, TN) hosted at the University of Pennsylvania.

### Study design and drug administration

This investigator-initiated, open-label study was conducted at the Hospital of the University of Pennsylvania, an urban quaternary academic medical center. The study was approved by the University of Pennsylvania's institutional review board, registered with ClinicalTrials.gov (NCT05102734), and conducted in accordance with the principles of the Declaration of Helsinki. Sample size was determined based on an anticipated 30% increase in TVD, and setting a one-sided α of 0.1, and ß of 0.8. A 1% topical nitroglycerin solution was prepared immediately prior to enrollment by reconstituting 400 mcg of nitroglycerin (Pfizer Pharmaceuticals, New York, NY, USA) in 4mL of sterile water within a dropper bottle that would administer the solution in 0.05mL aliquots. Two drops (0.1 mL) of the 1% nitroglycerin solution (5 mcg or 2.27\*10^-2 μmol per drop)

were applied to the sublingual space after obtaining baseline post-operative microcirculation images. A microdosing (approximately 1/50th of the lowest therapeutic sublingual dose) was administered to avoid any systemic effects.

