### Microcirculatory imaging and analysis

Sublingual microcirculation imaging was performed using HVM (CytoCam, Braedius Medical BV, the Netherlands) in the preoperative staging area (for controls) or within 2 hours of arriving to the intensive care unit after surgery by a trained member of the investigative team ([name] or [name]). The sublingual microcirculation was measured at 3 time points: baseline, 3 minutes post-nitroglycerin, and then 30 minutes later. Images were obtained by gently placing the videomicroscope under the subject's tongue until an adequate view of the microcirculation was obtained. A series of six second video clips (120 frames) duration were taken at each time point with attention to quality factors, especially the absence of pressure artifact, excess saliva, and proper location in accordance with the accepted consensus for microcirculation analysis. Image quality was assessed using the 6-factor Massey quality score, which scores each video for appropriate illumination, duration, focus, content, stability, and pressure. Images were only included in the final analysis if the Massey quality score was < 10 . Acceptable clips were deidentified and coded for analysis after enrollment was complete.

Microcirculation videos were exported using commercial software (CCTools 2, Braedius Medical BV, the Netherlands) and manually analyzed using the validated Automated Vascular Analysis software (AVA 3.2; Microvision Medical B.V., the Netherlands). Video analysis was performed by trained investigators ([name] and [name]) who were blinded to the conditions of the subject. Only microvessels <  $20 \, \infty m$  in diameter were included in the calculation of TVD and PVD.

Red blood cell flow velocity was calculated within appropriate venules 20-30 ∞m in diameter by manually measuring the slope of individual RBC movement within software generated space-time diagrams . Microcirculatory function was quantified according to the current best practice guidelines for microcirculation imaging. Blood flow within each microvessel was graded using a semiquantitative scale, based on the vascular flow pattern ranging from 0-3 (0=no flow, 1=intermittent, 2=sluggish, or 3=continuous flow). Vessel perfusion was dichotomized as nonperfused (no flow or intermittent flow) or perfused (continuous or sluggish) for the calculation of PPV and PVD.

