## Individual pharmacodynamic response to the nitroglycerin challenge

An exploratory analysis was planned to identify the incidence of a patient specific pharmacodynamic response to the nitroglycerin challenge. A PD response threshold was set as a post-administration PVD > 1.8 standard deviations from the baseline, which was calculated by averaging the intra-patient variance between the three baseline PVD video sequences, which was then pooled across the entire cohort. This 1.8SD threshold was set to achieve 90 percent confidence interval (assuming a one-sided alpha, since there was only an anticipated increase in PVD). This method has been used in previous Phase 0 trials to provide a statistically rigorous threshold for individualized PD responses to novel therapeutic interventions.

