### **Statistical Analysis**

Data normality was assessed using the D'Agostino-Pearson omnibus normality test. Global hemodynamic and microcirculation variables are reported as mean  $\pm$  SD. Variables that were not normally distributed are reported as median with interquartile range [ $25^{th} - 75^{th}$  percentiles]. Student t-test was used to test for differences between normally distributed variables. Mann-Whitney U test was used to analyze non-normal data. Repeated measure one-way ANOVA with Tukey's post-hoc testing was used to assess for changes in microcirculatory function during the nitroglycerin challenge. Inter-rater reliability between coders was assessed in 10% of the videos using a Bland-Altman plot. Statistical analysis was conducted using Prism v 8.0 (Graph-Pad Software, San Diego, CA). Statistical significance was assumed at p < 0.05.

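### The sample size statement mislabels β, and its one-sided 0.10 criterion does not match the p < 0.05 ANOVA/Tukey analysis, so no stated power applies to that analysis

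*Combined protocol and SAP*

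**What the plan says.** The sizing statement, under Study design and drug administration, is a single sentence: "Sample size was determined based on an anticipated 30% increase in TVD, and setting a one-sided α of 0.1, and ß of 0.8". It is not accompanied by a sample size, a standard deviation, a named test or a statement of which comparison was sized.

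The Statistical Analysis section assigns repeated-measures one-way ANOVA to the nitroglycerin challenge, and its Tukey "post-hoc testing was used to assess for changes in microcirculatory function during the nitroglycerin challenge". The threshold is given once, for everything: "Statistical significance was assumed at p < 0.05". Under Microcirculatory imaging and analysis, "The sublingual microcirculation was measured at 3 time points: baseline, 3 minutes post-nitroglycerin, and then 30 minutes later", so there are three pairwise Tukey comparisons.

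Two other passages leave the sized contrast open. Patient selection says "A second cohort of patients were enrolled to serve as a preoperative control", and the Statistical Analysis section also states "Student t-test was used to test for differences between normally distributed variables".

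The only other one-sided criterion is in the section on individual pharmacodynamic response, "assuming a one-sided alpha, since there was only an anticipated increase in PVD". It concerns an exploratory threshold for PVD in single patients, not the test of TVD.

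**The concern.** There are three linked problems.

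1. **β is mislabelled.** A β of 0.8 is a power of 0.2. Power of 0.8 (β = 0.2) is the likely intention, but the reader has to guess.
2. **The sizing and analysis criteria differ.** One-sided 0.10 requires a test statistic of 1.28. Every reading of the analysis threshold is stricter, and no passage says that the one-sided 0.10 level was meant for sizing only.
3. **The inputs are missing.** Without N, the SD, the sizing test and the sized contrast, the calculation can be neither reproduced nor carried over to the analysis actually used.

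What is at stake is the reading of a null result. A reader is likely to take 0.8 as the power behind a p < 0.05 test. It belongs, at most, to a one-sided 0.10 test that the analysis section does not describe. A non-significant TVD change would then carry less evidential weight than that figure suggests.

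**Working it through.** **Inputs from the documents.** Sizing: one-sided α = 0.10, β = 0.8 as written, 30% increase in TVD. Analysis: p < 0.05, repeated-measures ANOVA with Tukey, three time points. The documents state no N or power, so there is no figure of theirs to reproduce. What follows is conditional on N only just meeting the stated inputs.

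**Step 1: signal implied by the sizing inputs.** A design that just reaches the stated power has an expected effect, in standard errors, of z(1 − α) + z(power).

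- Power 0.8: 1.282 + 0.842 = 2.123.
- Literal β = 0.8 (power 0.2): 1.282 − 0.842 = 0.440.

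**Step 2: critical values at analysis.** The sidedness of p < 0.05 is not stated, so three readings are taken.

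- One-sided 0.05: 1.645.
- One two-sided 0.05 test: 1.960.
- One Tukey pair among three means, large degrees of freedom: q(0.95; 3, ∞)/√2 = 2.344.

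**Step 3: large-sample power**, Φ(signal − critical value), adding the opposite tail for two-sided tests where it matters.

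| Criterion | Power 0.8 intended | β = 0.8 taken literally |
|---|---|---|
| One-sided 0.10 (sizing) | 80% | 20% |
| One-sided 0.05 | Φ(0.478) = 68% | 11% |
| Two-sided 0.05 | Φ(0.163) = 56% | 6.4% + 0.8% = 7% |
| One Tukey pair | Φ(−0.221) = 41% | 2.8% + 0.3% = 3% |

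**Step 4: the omnibus F test.** Assume sphericity, a large sample and the 80% reading. If one time point differs from the other two by the full effect, the noncentrality is (4/3) × 2.123² = 6.01 on 2 degrees of freedom, and power is about 58%. If the third time point lies midway, the noncentrality is 2.123² = 4.51 and power is about 46%.

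**Step 5: small samples.** This uses a paired t test and the noncentral t distribution. The values of n are assumptions, not document figures. With power exactly 80% at one-sided 0.10:

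| Criterion | n = 6 | n = 30 |
|---|---|---|
| One-sided 0.05 | 63.9% | 67.7% |
| Two-sided 0.05 | 46.9% | 54.9% |
| Tukey pair, pooled error, 2(n − 1) df | 38.5% | 40.7% |
| Tukey pair, pair-specific error, n − 1 df | 29.9% | 39.0% |

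Rounding N up to a whole number raises these. At n = 6 the most favourable case has 86.5% design power, and then 72.6%, 55.9%, 48.3% and 37.5% in the same order. At n = 30 rounding adds at most about 1.5 percentage points.

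**Step 6: cost of the mismatch in patients.** In large samples, 80% power would need ((1.960 + 0.842)/2.123)² = 1.74 times the N at two-sided 0.05, or ((2.344 + 0.842)/2.123)² = 2.25 times for one Tukey pair. This is a measure of size, not a proposal to enrol more patients.

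**The case against.** The strongest reply has four parts.

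- **The β wording is probably only a slip of terminology.** Agreed. The literal-reading figures show what the text says as written, not what was probably done.
- **Sizing at a looser level than the analysis is not in itself an error, and a stricter test is conservative.** Also agreed: false positives are not inflated and a significant finding loses nothing. What remains is that the 0.8 cannot be attached to the p < 0.05 analysis, and the text does not say so.
- **Power is unknown because N and the SD are missing, not because the levels differ.** This is right as to cause. With those inputs, power at p < 0.05 could be computed despite the mismatch. But they are not there, and the only figure a reader has is for another criterion.
- **The Tukey figure may describe the wrong test.** A 30% increase suggests baseline against post-dose, but the t test and the matched control cohort leave other contrasts possible, and 41% is the power for one pre-chosen pair. This stands as a reason to treat 41% as conditional. It does not rescue the 0.8: under the same assumptions the omnibus F (about 58% or 46%) and a single two-sided test (about 56%) also fall well short of 80%.

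It is also true that no passage interprets a null TVD result or claims adequate power at 0.05. The risk lies in how the statement will be read.

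**Conclusion.** The concern holds and should be fixed. The sizing sentence is wrong as written on β. Even when it is read as 80% power, that power belongs to a one-sided 0.10 test rather than to the ANOVA/Tukey analysis at p < 0.05. Confidence in this textual mismatch is high.

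The size is conditional. If 80% was intended and N only just met the stated inputs, large-sample power at the design effect is about 41% to 68%, depending on which reading of the analysis applies. Small samples lower these figures and rounding N up raises them. The actual power cannot be derived from the documents.

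**What to change.** 1. Check the original calculation and, if it confirms the intention, correct the sentence to power 0.8 (β = 0.2).
2. State that the one-sided 0.10 criterion was used for sizing only and that the stated power does not apply to the p < 0.05 analysis.
3. Report N, the SD, the sizing test and the sized contrast, and restate power for a 30% TVD increase under the analysis actually used.
4. If those inputs cannot be recovered, make no power claim for the p < 0.05 analysis. Report the TVD change with its 95% confidence interval, Tukey-adjusted if it is one of the pairwise time contrasts.
5. Keep the p < 0.05 Tukey analysis. The text records that "Acceptable clips were deidentified and coded for analysis after enrollment was complete" and that the dataset is deposited, so loosening the threshold to match the sizing would be a change made after the data were available.

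The cost is wording plus one confidence interval from data already held: no new patients and no change of test or threshold. The price is that the stated power becomes less favourable or is withdrawn.

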### Microcirculatory imaging and analysis

Sublingual microcirculation imaging was performed using HVM (CytoCam, Braedius Medical BV, the Netherlands) in the preoperative staging area (for controls) or within 2 hours of arriving to the intensive care unit after surgery by a trained member of the investigative team ([name] or [name]). The sublingual microcirculation was measured at 3 time points: baseline, 3 minutes post-nitroglycerin, and then 30 minutes later. Images were obtained by gently placing the videomicroscope under the subject's tongue until an adequate view of the microcirculation was obtained. A series of six second video clips (120 frames) duration were taken at each time point with attention to quality factors, especially the absence of pressure artifact, excess saliva, and proper location in accordance with the accepted consensus for microcirculation analysis. Image quality was assessed using the 6-factor Massey quality score, which scores each video for appropriate illumination, duration, focus, content, stability, and pressure. Images were only included in the final analysis if the Massey quality score was < 10 . Acceptable clips were deidentified and coded for analysis after enrollment was complete.

Microcirculation videos were exported using commercial software (CCTools 2, Braedius Medical BV, the Netherlands) and manually analyzed using the validated Automated Vascular Analysis software (AVA 3.2; Microvision Medical B.V., the Netherlands). Video analysis was performed by trained investigators ([name] and [name]) who were blinded to the conditions of the subject. Only microvessels <  $20 \, \infty m$  in diameter were included in the calculation of TVD and PVD.

Red blood cell flow velocity was calculated within appropriate venules 20-30 ∞m in diameter by manually measuring the slope of individual RBC movement within software generated space-time diagrams . Microcirculatory function was quantified according to the current best practice guidelines for microcirculation imaging. Blood flow within each microvessel was graded using a semiquantitative scale, based on the vascular flow pattern ranging from 0-3 (0=no flow, 1=intermittent, 2=sluggish, or 3=continuous flow). Vessel perfusion was dichotomized as nonperfused (no flow or intermittent flow) or perfused (continuous or sluggish) for the calculation of PPV and PVD.

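### The plan removes clips on image quality and tests change by repeated-measures ANOVA, but makes no provision for a time point with no acceptable clip; a mixed model would use all acceptable time points at little cost

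*Combined protocol and SAP*

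**What the plan says.** All references are to the combined protocol and SAP.

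- **Microcirculatory imaging and analysis, time points.** The microcirculation is "measured at 3 time points: baseline, 3 minutes post-nitroglycerin, and then 30 minutes later".
- **Same section, clips.** "A series of six second video clips (120 frames) duration were taken at each time point". The number per time point is not given there. The section on individual pharmacodynamic response implies three at baseline, since its threshold comes from "averaging the intra-patient variance between the three baseline PVD video sequences".
- **Same section, quality filter.** The Massey score is applied clip by clip, "which scores each video for appropriate illumination, duration, focus, content, stability, and pressure", and "Images were only included in the final analysis if the Massey quality score was < 10". A clip scoring 10 or more is therefore excluded.
- **Statistical Analysis.** "Repeated measure one-way ANOVA with Tukey's post-hoc testing was used to assess for changes in microcirculatory function" during the challenge. "Statistical analysis was conducted using Prism v 8.0".

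The plan gives no minimum number of acceptable clips per time point, no method for an empty time point, no sensitivity analysis, no commitment to report excluded clips or patients, and no sample-size allowance for unusable images.

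**The concern.** A rule that removes images is paired with an analysis that needs a complete row of three values per patient. If every clip at, say, the 30-minute time fails, the classical ANOVA cannot use that patient at all. The comparison of baseline with 3 minutes then loses a patient for whom both values exist.

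Two things are at stake. The first is power. The second is who remains in the analysis. The quality score includes content, stability and pressure, and the patients who receive the drug are in postoperative shock, so image failure could plausibly be related to their condition. A complete-case analysis is generally safe when losses are completely at random. Some weaker patterns also do no harm: loss that depends on a stable patient trait unrelated to the change leaves the within-patient change unbiased. The plan does not say which situation it expects.

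**Working it through.** The plan states no figure that could be reproduced: it gives no sample size, SD or clip-failure rate. What follows shows only how the size depends on assumptions.

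**Inputs from the documents.** Three time points; a filter applied per clip; three baseline clips; sizing at one-sided α 0.10 with a stated β of 0.8, read here as 80% power.

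**Assumptions.** Three clips at every time point; clip-failure rate f of 10%, 20% or 30%; clip failures within a time point either independent or correlated with intraclass correlation (ICC) 0.3 or 0.6; time points independent of each other.

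**Step 1: chance q that a time point is empty.** Independent clips: q = f³. Correlated clips (beta-binomial): with s = 1/ICC − 1 and a = f·s, q = a(a+1)(a+2) / [s(s+1)(s+2)]. For f = 0.2 and ICC 0.3, s = 2.333 and a = 0.467, so q = 1.688/33.70 = 0.050.

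**Step 2: patients affected.** Share lacking at least one time point = 1 − (1 − q)³. Share lacking baseline or 3 minutes = 1 − (1 − q)².

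**Step 3: power.** Starting from 80% at one-sided 0.10, power = Φ(2.123·√(fraction kept) − 1.2816), where 2.123 = 1.2816 + 0.8416. "Complete cases" keeps (1 − q)³; "available pairs" keeps (1 − q)² for the baseline to 3-minute change.

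| ICC | f | q | Lacking ≥1 time | Lacking baseline or 3 min | Power, complete cases | Power, available pairs |
|---|---|---|---|---|---|---|
| 0 | 10% | 0.001 | 0.3% | 0.2% | 79.9% | 79.9% |
| 0 | 20% | 0.008 | 2.4% | 1.6% | 79.3% | 79.5% |
| 0 | 30% | 0.027 | 7.9% | 5.3% | 77.5% | 78.4% |
| 0.3 | 10% | 0.019 | 5.6% | 3.8% | 78.3% | 78.9% |
| 0.3 | 20% | 0.050 | 14.3% | 9.8% | 75.3% | 76.9% |
| 0.3 | 30% | 0.095 | 26.0% | 18.2% | 70.7% | 73.9% |
| 0.6 | 10% | 0.050 | 14.2% | 9.7% | 75.3% | 76.9% |
| 0.6 | 20% | 0.109 | 29.2% | 20.6% | 69.3% | 72.9% |
| 0.6 | 30% | 0.178 | 44.5% | 32.5% | 61.8% | 67.8% |

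**Step 4: the same by whole-time-point loss.** If 5%, 10% or 20% of time points are empty, independently, complete patients are 0.95³ = 86%, 0.90³ = 73% and 0.80³ = 51%. Usable baseline to 3-minute pairs are 90%, 81% and 64%. Power is 75%, 70% and 59% on complete cases against 77%, 74% and 66% on available pairs. With three independent clips, such losses would need clip-failure rates of about 37%, 46% and 58% (the cube roots of 0.05, 0.10 and 0.20), so they imply either clustering or very poor images.

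**Step 5: failures clustered within patient.** If the same patients fail at every time, the fraction kept is 1 − p under either method. Power is then 78%, 77% and 73% at p = 5%, 10% and 20%, and using available pairs gains nothing.

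The power figures are for a one-sided 0.10 test, as in the sizing statement. The planned analysis is ANOVA with Tukey tests at p < 0.05, so they show the scale of the loss and are not the power of that analysis.

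**The case against.** The strongest reply is that the documents already protect against an empty time point. Several clips are taken each time, the operator repositions until the view is good enough and watches for pressure and saliva, and patients who cannot tolerate imaging are excluded. If clips fail independently at 20% or less, at most 2.4% of patients are incomplete and power hardly moves. The documents contain no evidence that failures cluster. This stands as a limit on the size of the problem. It does not settle the matter: clips in one session share the operator, patient and probe position, so independence is the favourable assumption.

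It can also be said that the fix is modest. In Step 4 it recovers about 2, 3 and 7 points of power, and none under Step 5. It still uses only acceptable clips. That is correct, and it limits the benefit without making the change wrong.

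Three stronger readings are tempting, and the documents do not support them:

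- **That the plan drops patients.** This follows from the named method but is not stated; the text does not say how empty cells were handled in the software.
- **That one failed clip removes a patient.** The filter acts on clips, so a time point is lost only when all its clips fail.
- **That an incomplete patient leaves every analysis.** Only the ANOVA and its Tukey tests need all three times. The t-tests, Mann-Whitney tests and the responder analysis do not.

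**Conclusion.** The point holds as a gap with a cheap remedy. The plan filters clips on quality, names an analysis that needs every time point, and does not provide for a time point with nothing acceptable. Applied as written, the ANOVA and Tukey tests would leave out such patients, including from comparisons for which their data exist.

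The size cannot be determined from the documents. Under the assumptions above it runs from negligible (independent clip failures at 20% or less) to material (clustered failures: 14% to 29% of patients incomplete at 20% clip failure). A reader might infer that the trial lost a particular amount of power or that its sample was selected on severity. Neither is shown: no failure rate is reported, and a link between image failure and the patient's condition is plausible only.

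**What to change.** Replace "Repeated measure one-way ANOVA with Tukey's post-hoc testing" for the microcirculatory variables with a mixed model fitted by REML to patient-level means of the acceptable clips: time as a fixed effect, a random patient intercept, small-sample degrees of freedom, and Tukey-adjusted contrasts between times. Include every acceptable time point. State the minimum number of acceptable clips that defines a usable time point, and report the clips and patients excluded at each time. Show the complete-case ANOVA alongside as a sensitivity analysis.

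**Cost.** No new data are needed. Because the text is written in the past tense and refers to a deposited dataset, this means a small reanalysis as well as a change of wording. With complete data, the random-intercept model gives essentially the same result as the ANOVA.

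**Limit.** The model is valid under missing at random, which is weaker than missing completely at random. It recovers the available data but does not remove selection if image failure depends on the microcirculatory state that could not be seen. The counts of exclusions by time, and any difference between the two analyses, let a reader judge how much that could matter.

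### Clips pass the quality cut-off before they are deidentified, so the described blinding does not cover the choice of clips behind TVD and PVD

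*Combined protocol and SAP*

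**What the plan says.** Study design and drug administration describes the trial as open-label: "This investigator-initiated, open-label study was conducted at the Hospital of the University of Pennsylvania". The remaining steps are in Microcirculatory imaging and analysis, in this order:

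- **Recording.** Images are taken "by a trained member of the investigative team", with the probe held in place "until an adequate view of the microcirculation was obtained". Several clips are recorded at each time point, but no number is fixed.
- **Quality scoring.** The Massey score is applied, "which scores each video for appropriate illumination, duration, focus, content, stability, and pressure". Then: "Images were only included in the final analysis if the Massey quality score was < 10".
- **Coding.** "Acceptable clips were deidentified and coded for analysis after enrollment was complete".
- **Measurement.** Vessel analysis is done by trained investigators "who were blinded to the conditions of the subject".

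The section does not say who assigned the quality scores, when, or whether that person knew the time point or the group. No count of rejected clips is planned.

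The clips that remain supply TVD and PVD. They also feed the exploratory responder rule in the section on individual pharmacodynamic response: "A PD response threshold was set as a post-administration PVD > 1.8 standard deviations from the baseline". That rule takes its SD from three baseline sequences per patient.

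**The concern.** Blinded measurement protects only against bias that arises during measurement. If the decision to keep or drop a clip is made while its patient and time point can still be identified, that knowledge can influence which clips reach the blinded analysts.

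This matters here for three reasons. The nitroglycerin effect is a before-versus-after contrast with no randomized or placebo comparator. Only an increase in PVD was anticipated, so the expected direction was known. The controls are imaged in another setting, before surgery, so group as well as time point is apparent at recording. Blinded video analysis is the main protection described against assessment bias in TVD and PVD, and as written it begins one step too late.

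**Working it through.** **1. Order of steps.** The coding sentence has acceptable clips as its subject. A clip is acceptable once it has met the cut-off, so the natural reading is record, score, reject, code, measure. The only blinding statement belongs to the last step, and no other section masks the scoring. The gap follows from the text and needs no arithmetic.

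**2. What the documents cannot give.** They state no clip SD, no number of clips recorded and no rejection rate. What follows is an illustration of possible size. Assumptions: no true effect; independent clip values with SD 1; no other variation between times; three clips averaged per time point; upward selection after dosing only. Selection that is equal at both time points cancels.

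**3. Fixed cut-off applied selectively at one time point.** Let r be the share of clips rejected, rho the correlation of the quality score with TVD or PVD, z_r the r-quantile of the standard normal and phi its density. Then:

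shift = rho × phi(z_r) / (1 − r)

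| r | phi(z_r)/(1 − r) | rho = 0.25 | rho = 0.5 |
|---|---|---|---|
| 0.10 | 0.1755/0.90 = 0.195 | 0.049 | 0.097 |
| 0.25 | 0.3178/0.75 = 0.424 | 0.106 | 0.212 |
| 0.50 | 0.3989/0.50 = 0.798 | 0.199 | 0.399 |

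The shift is 0 at rho = 0.

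**4. Keeping the best three of K recorded clips.** The shift is rho times the mean of the three largest of K standard normal values.

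| K | rho = 0.25 | rho = 0.5 | rho = 1 (ceiling) |
|---|---|---|---|
| 4 | 0.086 | 0.172 | 0.343 |
| 5 | 0.138 | 0.277 | 0.553 |
| 6 | 0.176 | 0.353 | 0.703 |

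With K = 3 there is no choice and no shift.

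**5. Effect on the responder rule.** The plan's multiplier is reproduced as 1.2816 × √2 = 1.81, the one-sided 90% limit for a difference between two single measurements. For two three-clip means the SD of the difference is √(1/3 + 1/3) = 0.816. Without selection, P(difference > 1.8) = P(Z > 1.8/0.816 = 2.20) = 1.4%.

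Under the cut-off model the variance of a kept clip becomes 1 − rho² × L × (L − z_r), with L = phi(z_r)/(1 − r). At r = 0.50 and rho = 0.5:

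- Variance of a kept clip: 1 − 0.25 × 0.798 × 0.798 = 0.841.
- SD of the difference: √((0.841 + 1)/3) = 0.783.
- P(Z > (1.8 − 0.399)/0.783 = 1.79) = 3.7%.

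Across the table in step 3 the false-response rate runs from 1.6% to 3.7%. Perfect selection of three clips out of six gives 7.1% by simulation. All of these are below the nominal 10%.

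**The case against.** The strongest case against has four parts.

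- **The sequence is inferred.** It rests on one adjective in a retrospective sentence, and nothing shows that the scorer was unmasked. This is right as far as it goes. The point claims only that the described blinding does not reach selection, and a single sentence from the sponsor could settle who scored.
- **The cut-off is preset and no item is vessel density or perfusion.** On the stated order, the scorer also has no measured TVD or PVD. This narrows the scope for bias, and it stands. However, focus, content, stability and pressure call for judgment, no automated scoring is described, and the scorer can see the vessels.
- **The illustration departs from the plan.** The written cut-off applies to all images, no best-three-of-K rule appears anywhere, and the correlations and upward direction are assumed. This also stands. The figures show what differential selection could do, not that it happened. Because no SD is given, they cannot be set against the anticipated 30% rise in TVD.
- **The study appears complete.** Screening is dated August to October 2021 and the dataset is deposited. Reordering the steps may therefore no longer be possible, although reporting is, and so is blind re-scoring if the rejected recordings survive.

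**Conclusion.** The concern holds. Following the stated order leaves clip selection open to knowledge of time point and group, and no masking is described at that step. Whether bias occurred, and in which direction, cannot be determined from the documents.

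Under the stated assumptions, differential selection could move mean TVD or PVD by about 0.05 to 0.40 within-patient clip SD, and by up to 0.70 under perfect selection of three clips from six. It would move them by nothing if the score is unrelated to the outcome or if selection is equal at both times. The exposure lies mainly in the mean TVD and PVD comparisons. The exploratory responder count is less affected, since its false-response rate stays below 10% in every case examined.

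This should be corrected or clarified. Confidence is medium, because the order of steps is read from the text and the scorer's status is unknown.

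**What to change.** Deidentify and randomly code every recorded clip before any quality judgment, so that the code conceals time point as well as patient and group. The same blinded analysts then apply the existing Massey cut-off and the vessel analysis. Report clips recorded and rejected by time point and group.

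If the clips have already been selected:

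- Where rejected recordings were kept, re-score all clips blind and repeat the TVD and PVD comparisons as a sensitivity analysis.
- Where they were not kept, state who scored the clips and whether that person was masked.

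The cost is small. Two existing steps change order, some clips are coded and scored and then discarded, and no extra imaging is needed. Blind re-scoring depends on retained recordings, which the documents do not mention. None of this removes the operator's own selection at the moment of recording, which should be stated as a limitation.
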